Medical doctor will perform the procedure at the Temple University Hospital. If any medical assistance is needed, the medical doctor will be available.

9) Prior Approvals

No other approvals are necessary. This is a non-invasive, minimal risk procedure that can be performed in one visit.

10) Study Design

a) Recruitment Methods

Subjects will be recruited from the breast surgery clinic on a weekly basis until the required number of subjects has been enrolled. We will provide the consent form to the patient. No advertised will be used. No payment will be made to the subject.

b) Inclusion and Exclusion Criteria

Inclusion Criteria:

- Women who had mammogram and/or ultrasound Birads (category IV or V)
- Women ages between 30 and 80.
- Women who have been scheduled for biopsy from the Temple breast surgery clinic
- Women who have been scheduled for biopsy by [name].
- Women, who speak and understand English.

Exclusion Criteria:

- Women who do not meet the criteria requiring biopsy.
- Women who have allergic reaction to silicone.
- Women who cannot speak or understand English.
- Women who are pregnant.
- Women, younger than 30 years old, and older than 80 years old.

c) Local Number of Subjects

Less than 20 subjects will be enrolled.

d) Study-Wide Number of Subjects

INVESTIGATOR PROTOCOL TEMPLATE FOR MEDICAL STUDIES

Revised: Sept. 11, 2017

NA

e) Study Timelines

The subject will participate during one visit before biopsy. The study will remain open for one year. The preliminary analysis will be completed by December of 2016.

f) Study Endpoints

The study will end in one year. There are no secondary study endpoints.

g) Procedures Involved in the Human Research

Procedure:

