The patient should have had mammography or ultrasound by the time of this procedure. Once the doctor decides to perform biopsy, the tactile imaging will be planned. The breast scan, mammography, ultrasound, and biopsy are standard of care. The consent will be obtained before the biopsy. One of the investigators ([name] or [name]) will obtain the consent. Before the biopsy, the doctor will identify the mass(es) using other modalities such as an ultrasound. The tactile imaging sensor operator will obtain the tactile images. Then the biopsy will be performed. Radiology doctor, resident, and radiology technologist are always present during the procedure. In addition a professional assistant from the engineering group will operate the tactile imaging sensor. That person will not have any physical contact with the patient. The procedure will be very similar to the ultrasound device and it will be as follows:

- The patients will be lying on their back.
- The doctor will locate the mass using other modality (ultrasound or mammogram)
- The tactile imaging sensor will press the part of the breast where mass are located.
- An assistant will sketch the locations of the masses with the mass number.
- An assistant will operate the laptop to take image of the mass.
- The mass number will be noted with the images.
- The tactile imaging sensor will manually compress the mass with different force gently.
- The image will be taken and the mass number will be recorded.
- This procedure will be repeated until all the masses are imaged.
- This will take less than three minutes per mass.

INVESTIGATOR PROTOCOL TEMPLATE FOR MEDICAL STUDIES

Revised: Sept. 11, 2017

- After the tactile images are taken the doctor will perform the biopsy of the masses.
- The assistant will note the mass number and the order of the biopsy.
- The patient will receive standard biopsy results and a letter from the doctor.

Only one visit will be required for this study.

NOTE:

- None of the procedures done for research purposes involve radiation.
- The use or disclosure of protected health information involves no more than a minimal risk to the privacy of individuals. A unique subject identifier will be assigned to each subject. The subjects name and date of birth will be associated with the identifier and will be kept on a list and stored electronically in a secure password protected computer under the control of the Principal Investigator.

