All subjects will sign a written informed consent document. A signed and dated copy of the consent form will be given to each subject enrolled into the study.

“HRP-091 SOP: Written Documentation of Informed Consent” will be followed to document informed consent in writing.

19) Vulnerable Populations

None of the populations listed below will be recruited into the study

- Adults unable to consent
- Individuals who are not yet adults (infants, children, teenagers)
- Pregnant women
- Prisoners

20) Drugs or Devices

Only authorized investigators associated with the study will use the imaging sensor. When not in use, the sensor and associated equipment will be stored in a secure lock area in the Investigators office.

21) Multi-Site Human Research

This is a single-site study

Results of the study will not be shared with the subjects.

22) Statistical Data Analysis Plan

We will obtain 20 tactile image data sets from the breast tumor patients. The tactile images will be converted to size and deformation index. Then these two parameters will be converted to risk score, which is compared against pathology results. This is a small number of patients for statistically significance study. Therefore, we plan to use the Leave-One-Out-Cross-Validation (LOOCV) technique to validate the human test results to determine the performance of the device.

We obtain the Risk Score. Risk Score is a unit less numerical value, which can be used as a scale to classify the tumor as malignant and benign. Based on the calculated size of the tumor and measured deformation index, the breast tumors are classified as benign and malignant using scoring method. The risk score will range

INVESTIGATOR PROTOCOL TEMPLATE FOR MEDICAL STUDIES

Revised: Sept. 11, 2017

from 0 to 5, where 0 represents the benign and 5 represents the malignant tumor. A marginal threshold value was set, where any risk score below threshold is considered benign. The calculated risk score is based on the below equation,

$$RiskScore = \left[\left(\frac{W_1 \times S}{S_{max}} - \frac{W_2 \times DI}{DI_{max}} \right) \right] R,$$

where, W_1 and W_2 are the two weights used for size and deformation index respectively, S represents the estimated size value, S_{max} is the maximum estimated size value, DI is the calculated deformation index, DI_{max} is the maximum calculated deformation index. R is the range of risk score used.

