Comparing the Risk Score and the Pathology reports we obtain the following measures. The sensitivity, specificity and accuracy of the system have to be measured to know the reliability of the device. These system performance parameters helps to evaluate the performance of device, which is calculated based on the Risk Score using the below equations,

$$Sensitivity_{CISS} = \frac{TP}{TP + FN} (\%),$$

$$Specificity_{CISS} = \frac{TN}{TN + FP} (\%),$$

$$Accuracy_{CISS} = \frac{TN + TP}{TN + FP + TP + FN} (\%).$$

The positive result shows the presence of malignant tumor whereas the negative result implies the presence of benign tumor. TP , TN , FP , and FN represent true positive, true negative, false positive and false negative cases respectively. False positive is considered to be a case where benign masses are classified as malignant, whereas false negative are cases where malignant masses are classified as benign. True positives are the correctly classified malignant cases. True negatives are the correctly classified as benign cases.

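### Section 22 uses LOOCV in place of a significance assessment, but LOOCV does not show whether the reported accuracy exceeds chance, and the plan supplies no chance reference

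*Combined protocol and SAP*

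**What the plan says.** Section 22 (Statistical Data Analysis Plan) says of the sample: "This is a small number of patients for statistically significance study". It draws this consequence: "Therefore, we plan to use the Leave-One-Out-Cross-Validation (LOOCV) technique to validate the human test results to determine the performance of the device". Size and deformation index are combined into a risk score, and masses below a threshold are called benign. The calls are compared with pathology: "The sensitivity, specificity and accuracy of the system have to be measured to know the reliability of the device". Three percentages are defined. No chance value, confidence interval, test or success criterion accompanies them.

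The rule itself is not fully specified. On the cut-off, the plan says: "A marginal threshold value was set, where any risk score below threshold is considered benign". On the weights it says only that "W_1 and W_2 are the two weights used for size and deformation index respectively". It gives neither the values nor what, if anything, is re-estimated when a case is left out.

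The number of units is also unsettled. Section 22 says "We will obtain 20 tactile image data sets from the breast tumor patients", while Section 10(c) says "Less than 20 subjects will be enrolled". Under Section 10(g) one woman may contribute several masses: "This procedure will be repeated until all the masses are imaged".

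**The concern.** The step from a small sample to LOOCV does not follow. LOOCV answers one question: how much does performance fall when a rule is applied to a case that did not help to build it? A significance assessment answers another: could a score unrelated to pathology have produced this result? Small samples make the second question more pressing, and cross-validation leaves it open.

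Readers will tend to judge a cross-validated accuracy against 50%. Under LOOCV with tuning, that need not be the chance value. The chance value depends on the malignant/benign split and on the tuning rule, and the plan states neither. An accuracy in the low seventies could therefore be reported as device performance when the sensor carries no information.

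**Working it through.** **1. Plan's own figure.** There is none to reproduce. Section 22 gives no power, error rate, null value or target accuracy.

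**2. Inputs.** From the documents: at most 19 women (Section 10(c)) or 20 data sets (Section 22), and a score formed from weighted size S minus weighted deformation index DI. Assumed, because the documents do not say:
- the malignant/benign split;
- S and DI unrelated to pathology, with assumed distributions;
- masses independent of one another;
- W1 on an 11-point grid with W2 = 1 − W1;
- weights and cut-off refitted in each fold, by training accuracy or by Youden's index.

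**3. If nothing is refitted.** LOOCV returns the same calls as the fixed rule. With malignant share p and share q called malignant, chance accuracy is pq + (1 − p)(1 − q), which is 50% when q = 0.5. Then:
- 20 masses: P(at least 14 correct) = 60,460 / 2^20 = 5.8%.
- 19 masses: 70% of 19 is 13.3, so 14 are needed (73.7%). P = 16,664 / 2^19 = 3.2%.

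**4. Why refitting moves the centre.** Take the extreme rule that calls the left-out mass by the majority class of the rest.
- 6 malignant, 13 benign: leaving out a malignant mass gives 5 against 13, so the call is benign and wrong. Leaving out a benign mass gives 6 against 12, so the call is benign and right. Accuracy is 13/19 = 68% with no information used.
- 10 and 10: the left-out class is always the minority (9 against 10), so every call is wrong and accuracy is 0%.

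A rule tuned on accuracy is pulled towards these extremes.

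**5. Simulation, useless score, 19 masses, 6,000 data sets per setting.** Binomial SD = √(p(1 − p)/19) at the simulated mean p, for example √(0.426 × 0.574/19) = 0.113.

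| Malignant/benign | Tuned on | Mean accuracy | SD | Binomial SD | Variance ratio | Accuracy at least 70% |
|---|---|---|---|---|---|---|
| 6/13 | accuracy | 60.6% | 0.099 | 0.112 | 0.78 | 11.2% |
| 6/13 | Youden | 50.6% | 0.160 | 0.115 | 1.93 | 9.6% |
| 9/10 | accuracy | 42.6% | 0.189 | 0.113 | 2.78 | 4.6% |
| 9/10 | Youden | 50.2% | 0.143 | 0.115 | 1.55 | 5.8% |

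Other runs of the same design gave the same picture: means of about 43–60%, 95th percentiles of 74–79%, and 5–15% of trials at 70% or more. At 6/13 with accuracy tuning, the SD in those runs (0.107 to 0.110) was close to binomial (0.112 to 0.113).

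**6. Same check with 20 masses** (threshold alone, or weights and threshold, refitted):
- Youden tuning: variance 1.6 to 2.9 times binomial; 9–23% reach 70%.
- Accuracy tuning, 8 or 10 malignant: variance 1.2 to 3.9 times binomial; 5–9% reach 70%.
- Accuracy tuning, 5 or 6 malignant: variance 0.35 to 0.69 times binomial; 33–77% reach 70%. Calling every mass benign already scores 15/20 = 75% or 14/20 = 70%.
- Fixed rule calling half the masses malignant: SD 11.1 to 11.2 points; 5.7–5.8% reach 70%, which agrees with step 3.

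**7. Does a permutation test work at this size?** Shuffling labels and rerunning the whole LOOCV (20 masses, accuracy as statistic, 199 shuffles, 400 data sets per setting) rejected a useless score in 2.2–5.0% of data sets at the nominal 5%. A set of 999 shuffles took about 0.2 seconds. Power was limited:
- Combined AUC about 0.79, same design: 25–38%.
- AUC 0.85, mean of sensitivity and specificity as statistic, 19 masses, Youden tuning: 49% (6/13) and 54% (9/10).
- AUC 0.90, same design: 64% and 70%.

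**The case against.** Four objections carry weight.

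*The tuning is assumed.* The past tense used for the threshold may mean it is already fixed, and no passage says that anything is refitted. This stands. If the weights are fixed too, steps 4 to 6 do not apply. But then LOOCV, the plan's only response to the small sample, does no work, and a chance reference is still missing.

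*Sensitivity and specificity are reported too.* A rule that drifts to benign would show very low sensitivity. This stands in part. Both measures reached 70% by chance in only 0.3–4.5% of null data sets at 20 masses, and in 0.3–2.8% at 19. The risk therefore lies mainly in accuracy. The plan sets no requirement on the pair, however, and still reports accuracy as a headline measure.

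*The plan is right that the sample is small.* It is, as regards power. A reader might infer that an exact test would have good power, since a two-sided rank-sum test at 19 masses reaches 76–82% at AUC 0.85 and 91–94% at AUC 0.90. Those figures belong to a rank-sum test on a fixed score. The LOOCV permutation test is weaker (step 7) and cannot borrow them. Low power makes an inconclusive result likely, but it does not make cross-validation a substitute for a test.

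*This is a small exploratory study.* Section 11 rules out diagnostic use of the device and any claim that it is effective. That limits the consequences of a misleading figure. It does not make the figure interpretable.

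**Conclusion.** The point holds, and the plan should be changed. LOOCV is put where a chance assessment belongs, and the reported percentages cannot be read without one. With 19 masses and refitting in each fold, chance accuracy centres between roughly 43% and 60%, and 70% or more arises in roughly 5–15% of trials of a useless score. The malignant share, feature distributions, tuning rule and independence of masses are assumptions. The qualitative conclusion rests only on the absence of a reference.

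Two stronger readings are not supported. A reader might infer that LOOCV percentages always vary more than a binomial count. They do under Youden tuning or near-balanced classes. With accuracy tuning and few malignant masses the spread is about equal to binomial or narrower, and the problem there is the majority-class baseline (13/19 = 68%). With a fixed rule the binomial reference holds. A reader might also infer that a permutation test is a complete remedy at no cost. It tests only for no association, gives no interval for sensitivity or specificity, and cannot be run until the fitting steps are specified.

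**What to change.** In Section 22, keep LOOCV and make these changes:

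1. State what is refitted in each fold (weights, cut-off, maxima used for scaling) and by which criterion, or state that nothing is.
2. Beside the observed sensitivity, specificity and accuracy, print the accuracy of calling every mass benign and of calling every mass malignant.
3. Add a permutation test of the entire tuning-plus-LOOCV procedure with at least 2,000 label shuffles, using the mean of LOOCV sensitivity and specificity as the statistic. Keep each woman's masses together, and say how women with several masses are handled. Report the null mean, null 95th percentile and p-value. If nothing is refitted, use an exact test instead.
4. Replace the remark about the small number with a statement that the test controls its error rate at this size but has limited power, so a non-significant result is inconclusive. Do not attach rank-sum power figures to it.

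The cost is wording and a short loop in the analysis code, with no new data. The downside for the sponsor is that an accuracy near 70% may no longer be presentable as evidence that the device works.
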